**19.4. APPENDIX D: Subject Forms**

Site-specific Patient Informed Consent (PIC) templates will be retained in a separate document from the body of the clinical investigation plan document. This will be provided to investigational sites and updated as necessary.

### 19.5. APPENDIX E: Subject Enrollment Decision Tree

---

## 20. Version History

Version	Summary of Changes	Author(s)/Title
1.0	'Not Applicable, New Document'	[REDACTED] Senior Medical Writer
2.0	
 
▪ Minor typos correction
 
▪ Title: Correction of the title, subject has replaced patient by error in version 1.0.
 
▪ Front page: Confidentiality Statement: added Sofradim Production to indicate relationship with Medtronic plc.
 
▪ Section 2. Deletion of FAS definition as it is not used in the CIP, correction of PPAS definition and addition of PAS and SAS definition.
 
▪ Section 3. Update of synopsis for the title and statistical section
 
▪ Section 6.1. Addition of the use of the AE report form for safety reporting to be complaint with section 11.
 
▪ Section 9.6. Correction of example for major deviation
 
▪ Section 9.7.2 and 9.7.4 Clarification that screen failure and withdrawal will also be recorded in the POETRY Study Exit Form.
 
▪ Section 9.7.3. Addition that reason for discontinuation will be clearly recorded in the applicable POETRY Study Exit Form and Club Hernie Registry Database
 
▪ Section 9.7.5. Clarification that attempts to contact Lost to Follow-Up patient must be documented.
 
▪ Section 11.1.6. Addition of RA Medtronic France email.
 
▪ Section 11.2. update of study email for the reporting of AE.
 
▪ Section 11.3 Study Contact Information update
 
▪ Section 13. Addition of Per Protocol Analysis Set definition
 
	[REDACTED] Clinical Study Manager
3.0	Appendix B. Update of IFU	[REDACTED]
	
 
▪ Change of template 056-F275, v A Clinical Investigation Plan Template
 
▪ Section 2. Addition of EU MDR definition
 
▪ Section 3. Clarification of Clinical Study type
 
	[REDACTED] Clinical Study Manager

	

▪ Section 3. Update of inclusion/exclusion criteria and Study Procedures and Assessments per change in section 8.2, 8.4 and 9.1.2

▪ Section 5. Update of section title per new template

▪ Section 6. Change of sub-section categories per the new template

▪ Section 8.3. Clarification of the risk factors linked to hernia history

▪ Section 8.4. Clarification of exclusion criteria #2 by highlighting two contra-indications

▪ Section 9.1.2 Addition of the pregnancy test (for exclusion criteria)

▪ Section 9.7.2 Deletion of record of screen Failure in the Club Hernie database

▪ Section 11.2. Addition of reporting requirement to RA Medtronic France per 056-G140 Global Safety Reporting Requirements for Clinical Studies

▪ Section 14.1 Addition of the EU MDR for study compliance

	
4.0	

▪ Change of template 056-F275, v B Clinical Investigation Plan Template

▪ Document updated for ISO14155:2020

▪ Document updated to allow for up to 12 sites

▪ Document updated for minor typos

▪ Document updated to clarify Sponsor vs Local Sponsor

▪ Glossary updated to include additional terms and abbreviations

▪ Section 1 Investigator Statement is now called the Investigator Commitment

▪ Section 4 Synopsis section updated to reflect document changes

▪ Section 6.2.2 updated to include additional secondary endpoint

▪ Section 7 Study Design has been updated

▪ Section 7.3 Study Oversight section added

▪ Section 8 Product Description updated to include additional meshes

▪ Section 8.5 updated to clarify product training requirements

	[REDACTED], Senior Medical Writer

	

▪ Sections 8.7 Product Storage added

▪ Section 8.8 Product Return and 8.9 Product Accountability have been updated

▪ Section 9 Study Site Requirements added

▪ Section 10.2 Subject Enrollment has been edited for clarity

▪ Section 10.3 Inclusion Criteria has been updated

▪ Section 10.4 Exclusion Criteria has been updated

▪ Section 11.1 Schedule of Events has been updated

▪ Section 11.2 Data Collection has been updated

▪ Section 11.2 Table 2 updated to clarify adverse event collection to occur at all visits

▪ Section 11.3 Scheduled Follow-up Visit Windows has been added

▪ Section 11.5 Subject Consent updated

▪ Section 11.7 Scheduled Follow-up Visits has been edited for clarity

▪ Section 11.8 Subject Questionnaires has been added

▪ Section 11.11 Recording Data has been updated

▪ Section 11.12 Deviation Handling has been updated

▪ Section 11.13.1. Study Exit has been updated

▪ Section 11.13.5 Lost to Follow-up has been updated with details

▪ Section 11.13.6 updated to clarify when to exit a subject if a mesh has been removed

▪ Section 11.13.7 Study Completed has been added

▪ Section 12.1 Potential Risks has been updated

▪ Section 12.2 Risk Minimization has been updated

▪ Section 13 Adverse Events and Device Deficiencies updated

▪ Section 13.1 updated to clarify procedure related adverse events

▪ Section 13.8 Subject Death added

▪ Section 13.9 Product Complaint Reporting added

▪ Section 14 Data Review Committees updated

▪ Section 15 Statistical Design and Methods updated

	
--	---	--

	

▪ Section 15.3. updated to allow for an additional interim analysis

▪ Section 16.1 Statement(s) of Compliance updated

▪ Section 17.1 Monitoring updated for remote monitoring

▪ Section 17.2 Data Management has been updated

▪ Section 17.3 Direct access to Source Data/Document updated

▪ Section 17.8 Reporting requirements added

▪ Section 17.10 Suspension or Early Termination updated

▪ Appendix B added in additional IFU for additional meshes

▪ Appendix E Subject Enrollment Decision Tree added

	
--	---	--

V2.0 – 05Nov2021	
 • Update of CIP version page 1 (V4.0) • Add Pregnancy Test (Section 5 page 7) • Demographic, risk factors and per-operative characteristics: measured on PAS, PPAS, SAS removed from Secondary Endpoints (alignment with CIP V4.0). • Update of Section 7.10 Safety evaluation is covered by secondary endpoints. 
Listing of AEs, SAEs, ADEs and SADEs, and U(S)ADEs will be provided based on Safety Analysis Set. AEs, SAEs, ADEs and SADEs, and U(S)ADEs will be analyzed using Medical Dictionary for Regulatory Activities (MedDRA v23.1) classification per System Organ Class and Preferred Term and they will also be assessed using the potential risks identified in the Clinical Investigation Plan.
 
An Adverse Device Effect is an Adverse Event related to device and/or procedure.
	[REDACTED] Sr Biostatistician, Surgical Innovations Medtronic

2. List of Abbreviations and Definitions of Terms

Term/Abbreviation	Definition
ADE	
Adverse device effect - Adverse event related to the use of an investigational medical device.
 
Note: This definition includes adverse events resulting from insufficient or inadequate instructions for use, deployment, implantation, installation, or operation or any malfunction of the investigational medical device.
 
Note: This definition includes any event resulting from use error or from intentional misuse of the investigational medical device.

Term/Abbreviation	Definition
AE	
Adverse event - Any untoward medical occurrence, unintended disease or injury, or untoward clinical signs (including abnormal laboratory findings) in subjects, users or other persons, whether or not related to the investigational medical device.
 
Note: This definition includes events related to the investigational medical device or the comparator.
 
Note: This definition includes events related to the procedures involved.
 
Note: for users or other persons, this definition is restricted to events related to investigational medical devices.

CI	Confidence Interval
CIP	Clinical Investigation Plan (can be used synonymously with Protocol)
Hernia	A clinically manifested bulge or a protrusion exacerbated by a Valsalva maneuver.
PAS	Performance Analysis Set
PMCF	Post Market Clinical Follow up
PPAS	Per Protocol Analysis Set – An analysis set a subset of the Performance analysis set, excluding subjects with major protocol deviation(s) and violation(s).
QOL	Quality of Life
SAE	
Serious Adverse Event - Adverse event that:
 
 a) Led to a death, b) Led to a serious deterioration in the health of the subject, that either resulted in: 
 1) Resulted in a life-threatening illness or injury, or 2) Resulted in a permanent impairment of a body structure or a body function, or 3) In-patient or prolonged hospitalization, or 4) Medical or surgical intervention to prevent life threatening illness or injury or permanent impairment to a body structure or a body function, or 
Led to fetal distress, fetal death or a congenital abnormality or birth defect.
 
Note: Planned hospitalization for a pre-existing condition, or a procedure

Term/Abbreviation	Definition
	required by the CIP, without serious deterioration in health, is not considered a serious adverse event.
SADE	Serious Adverse Device Effect - Adverse device effect that has resulted in any of the consequences characteristic of a serious adverse event.
SAP	Statistical Analysis Plan
SAS	Safety Analysis Set – An analysis set including any subjects enrolled in the study.
USADE	Unanticipated Serious Adverse Device Effect - Any serious adverse device effect which by its nature, incidence, severity or outcome has not been identified in the current version of the risk analysis report. Note: Anticipated serious adverse device effect (ASADE) is an effect which by nature, incidence, severity or outcome has been identified in the risk analysis report.
VAS	Visual Analog Scale is a psychometric response scale (0-10) which can be used in questionnaires to determine how much pain a subject is feeling.

3. Introduction

Although laparoscopic minimally invasive surgeries have increased in frequency, midline laparotomies are still common in both elective and emergency cases. After midline laparotomy, the prevalence of incisional hernias ranges between 10% and 54% depending on if the procedure was elective or emergency. (1-3) The presence of an incisional hernia can lead to complications such as bowel obstruction, incarceration, strangulation, and/or patient discomfort and pain. (4) Repair of incisional hernias requires additional procedure adding additional risk to the patient and financial costs. As a result, prevention of incisional hernias has become a common goal and in recent years, multiple studies have shown decreased frequency of incisional hernias when using prophylactic polypropylene mesh after midline laparotomies.

To that end, based on the expansive vast long-term data attained during the development of multiple surgical meshes for use in a variety of soft tissue repairs, Medtronic has developed the ProGrip™ self-gripping polyester mesh. Composed of knitted monofilament polyester with polylactic acid monofilament resorbable pins ProGrip™ self-gripping polyester mesh is intended for use in reinforcement of soft tissue where weakness exists, in procedures involving the repair of inguinal and incisional hernias or abdominal suture line reinforcement.

Medtronic has conducted a biocompatibility evaluation of ProGrip™ self-gripping polyester mesh, compliant with the standard EN ISO 10993-1 (2009), which demonstrates the biological safety of the device. Pre-clinical animal testing of ProGrip™ self-gripping polyester mesh demonstrates that the mesh shows the same inflammatory reaction as Parietex™ mesh (#0607CR023), similar gripping power to ProGrip™ self-gripping polypropylene mesh (#0607CR027) and contributes to the fixation of the mesh to the surrounding tissues better than Parietex™ mesh (#MC2009-004CR020). ProGrip™ Self Gripping Polyester has been available for use in inguinal and incisional hernia repair since 2008 and the available clinical data support a positive risk/benefit ratio.

The purpose of this study is to confirm the efficacy and safety of ProGrip™ Self-gripping Polyester Mesh for suture line reinforcement to reduce the incisional hernia incidence within 24 months in a minimum of 135 enrolled subjects undergoing procedures with midline laparotomies.

4. Study Objectives

4.1. Primary Objective

The primary objective of this investigation is to confirm the efficacy of ProGrip™ Self-gripping Polyester Mesh to reduce the incidence of incisional hernia within 24 months post-operatively in subjects undergoing procedure with midline laparotomies.

4.2. Secondary Objective

The secondary objective of this investigation is to confirm the safety of ProGrip™ Self-gripping Polyester Mesh through the occurrence of adverse device effects or procedure related adverse events following the use of ProGrip™ Self- gripping Polyester Mesh in subjects undergoing procedures with midline laparotomies.

5. Investigation Plan

This study is a prospective, multicenter, PMCF embedded registry study evaluating the use of the ProGrip™ Self-gripping Polyester Mesh in subjects undergoing midline laparotomy in order to prevent incisional hernia using the embedded registry data of Club Hernie in France.

The Club Hernie is a non-profit organization created in 2009, currently including 40 French surgeon permanent members, with the aim to improve the healthcare treatments in parietal surgery by an assessment of surgical

practices, promoting research in abdominal wall surgery using an internet database open to surgeon members to monitor their own hernia practice and outcomes.

This study utilizes the Club Hernie established registry database. This online database consists of systematic and consecutive data entry of all subjects treated for abdominal wall surgery with standard data captured of all preoperative, perioperative and post-operative data.

Subjects who meet the eligibility criteria will be considered for study participation and will be evaluated at screening/baseline, procedure, Day 1, discharge, Day 8, and 1, 12, and 24 months post-surgery. Enrollment period planned is 22 months in up to 12 sites in France. For this study Club Hernie permanent members, non-permanent and new members are considered for participation.

The duration of the study is estimated to be up to 46 months (22 months enrollment and 24 months follow-up). Screening for subject eligibility may occur up to 30 days (inclusive) prior to the procedure and post-procedure subjects will be assessed at Day 1, discharge, Day 8, and 1, 12, and 24 months. In total, subjects will participate in the study for a maximum of approximately 26 months, following the study schematic below:

Procedure/Assessment	Screening (Day -30 to 0)	Operative (Day 0)	Post-operative course (Day 0) Follow up	Post-operative course (Day 1) Follow up	Discharge Assessment	Post-operative course (Day 8, +/-2days) Follow Up	1 Month (Day 30, +/-1week) Follow-up	12 Months (-1/+4 weeks) Follow-up	24 Months (-1/+4 weeks) Follow-up
	Can be combined								
Eligibility criteria	X ¹	X ¹							
Informed consent	X ²								
Pregnancy Test	X								
Subject demographics	X								
Relevant prior medical/surgical history	X								
Surgical Data									
Date of surgery		X							
Procedure indication		X							
Surgical technique for laparotomy closure		X							
Mesh reference and lot number		X							
Type of fixation		X							
Operative time		X							

Procedure/Assessment	Screening (Day -30 to 0)	Operative (Day 0)	Post-operative course (Day 0) Follow up	Post-operative course (Day 1) Follow up	Discharge Assessment	Post-operative course (Day 8, +/-2days) Follow Up	1 Month (Day 30, +/-1week) Follow-up	12 Months (-1/+4 weeks) Follow-up	24 Months (-1/+4 weeks) Follow-up
	Can be combined								
Mesh positioning and time		X							
Peri-operative events including adverse device effects or procedure related adverse events		X							
Surgeon satisfaction		X							
Post-operative data									
VAS pain assessment			X	X		X	X	X	X
Post-operative adverse events				X	X		X	X	X
Date of discharge					X				
Length of Hospital stay					X				
Physical exam including hernia clinical examination							X	X	X
Abdominal CT Scan								X	X
Quality of Life Questionnaire							X	X	X
Patient Satisfaction								X	X
1-month prior phone call including self-assessments								X	X
Study Exit									X
1. If Screening and Surgery occur on different days, these procedures should occur during Screening and be reconfirmed on the day of surgery. 2. No study procedures will be performed until informed consent form has been completed. Subject should be re-consented if date of original consent is greater than 30 days.									

6. Determination of Sample Size

Sample size is determined based on primary performance endpoint, assuming the superiority of ProGrip™ Self-gripping Polyester Mesh use to prevent incisional hernia vs no prevention of incisional hernia within 2-years following a midline laparotomy procedure.

The literature review showed an incisional hernia rate after midline laparotomies around 20% (9-16). Using a power ($1-\beta$) of 80% and a 5% error type I (two-sided), and considering a hypothetical incisional hernia rate of 10% for subjects with ProGrip™ Self-gripping Polyester Mesh, vs a theoretical hypothetical incisional hernia rate of 20% for subjects without any prevention following a midline laparotomy procedure, N= 108 evaluable subjects are required.

Assuming an attrition rate of 20% at 2-years, N=135 subjects will need to be enrolled.

7. Statistical Methods

7.1. Study Subjects

7.1.1. Disposition of Subjects

Summaries of consented/screened, screen-failures and enrolled subjects will be provided overall. Screen failures reason(s) will be reported.

Subjects in the Safety Analysis Set (SAS), in the Performance Analysis Set (PAS) and in the Per Protocol Analysis Set (PPAS) will be summarized, according to follow-up.

Reason for study discontinuation will be tabulated based on Safety Analysis Set, Performance Analysis Set and Per Protocol Analysis Set.

7.1.2. Clinical Investigation Plan (CIP) Deviations

Subjects with protocol deviations will be summarized; protocol deviations (minor/major) and violations will be reported by type on both Safety Analysis and Performance Analysis Sets.

Major protocol deviations and violations will be defined and identified by the study team prior to run statistical analysis, based on protocol deviations listing provided by statistician.

7.1.3. Analysis Sets

Statistical analysis will be performed on:

- Performance Analysis Set (PAS): includes all enrolled subjects excluding subjects who became pregnant during the follow-up, or subjects who undergo unscheduled abdominal surgery during study follow-up, which may increase the risk and cause of incisional hernia occurrence*.

*Subject follow-up data, starting from the event's occurrence, will be excluded/remove from the performance analysis.

- Per Protocol Analysis Set (PPAS): a subset of PAS excluding subjects with protocol violation and major protocol deviation(s) that may impact the primary endpoint assessment. More precisely, reason for exclusion may include but is not limited to:
 - Patient wrongly included (*i.e.* patient was enrolled but does not meet all the eligibility criteria).
 - Failure to obtain informed consent.
 - Deviation resulting from device use outside the recommended use in the IFU.
 - Patient who receives the incorrect device or device is misused
- Safety Analysis Set: includes all enrolled subjects.

Performance analyses will be run on Performance Analysis Set (PAS) and on Per Protocol Analysis Set (PPAS) as confirmatory analysis.

Safety analyses will be run on Safety Analysis set (SAS) and on Per Protocol Analysis Set (PPAS), as confirmatory analysis.

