# 15. Statistical Design and Methods

## 15.1 General Aspects of Analysis

For each of the objectives the available data will be summarized and missing data will be discussed. The main analysis of the study objectives will be based on available data and missing data will not be imputed unless otherwise noted in the statistical analysis plan. All practical monitoring and follow-up steps will be taken to ensure complete and accurate data collection. Deviations to the statistical analysis plan (SAP) will be reported per section 11.12 (Deviation Handling).

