7.4. Handling of Missing, Unused, and Spurious Data and Dropouts

No data imputation will be performed for missing data unless otherwise noted in statistical analysis plan. All practical monitoring and follow-up steps will be taken to ensure complete and accurate data collection.

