7.9. Evaluation of Objectives

Primary Objective and Endpoint

The primary objective of this investigation is to confirm the efficacy of ProGrip™ Self-gripping Polyester Mesh to reduce the incidence of incisional hernia within 24 months post-operatively in subjects undergoing procedure with midline laparotomies.

The primary endpoint is the incisional hernia rate within 24 months of midline laparotomy assessed by CT-scan and physical examination including hernia clinical examination.

Statistical analysis of primary endpoint will be comparative. Binomial one-way test will be used to compare the observed ProGrip™ Self- gripping Polyester Mesh incisional hernia incidence rate to the 20% theoretical incidence rate (from no prevention population), using a two- sided alpha-level of 5%.

Primary endpoint will be measured using Performance Analysis Set; a confirmatory analysis of primary endpoint will be run using Per Protocol Analysis Set.

Secondary objective and endpoints

The secondary objective of this investigation is to confirm the safety of ProGrip™ Self-gripping Polyester Mesh through the occurrence of adverse device effects or procedure related adverse events following the use of ProGrip™ Self-gripping Polyester Mesh in subjects undergoing procedures with midline laparotomies.

To confirm the safety of ProGrip™ Self-gripping Polyester Mesh through the occurrence of adverse device effects or procedure related adverse events following the use of ProGrip™ Self-gripping Polyester Mesh in subjects undergoing procedures with midline laparotomies.

The following secondary endpoints will be assessed:

- Adverse event (AE) incidence reported by number, severity, seriousness and relationship to the procedure and device from the surgery to the 24-month visit: AE incidence will be measured on Safety Analysis Set.
- Time to incisional hernia occurrence: will be measured using Kaplan Meier estimates, and based on SAS, and PPAS.
- Post-operative pain at the site of surgery: will be measured on SAS and PPAS, at each postoperative timepoint: Day0 (after surgery), Day1, Day8, Day30, Month12 and Month24.
- Quality of life: will be measured on all, PAS, SAS, and PPAS, using Club Hernie QOL questionnaire, combining qualitative and quantitative data, at Month1, Month12 and Month24.
- Patient satisfaction: at 12 then 24 months, measured on PAS, PPAS and SAS
- Surgeon satisfaction, measured on PAS, SAS, and PPAS

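### The Performance Analysis Set pairs whole-subject exclusion with a footnote that only truncates data, and either rule can remove a true incisional hernia from the primary analysis

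*SAP*

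**What the plan says.** SAP 7.1.3 builds the Performance Analysis Set (PAS) from all enrolled subjects, then leaves out those who became pregnant and "subjects who undergo unscheduled abdominal surgery during study follow-up, which may increase the risk and cause of incisional hernia occurrence". An asterisk on that clause leads to a footnote under which follow-up data, counted from the moment of the event, "will be excluded/remove from the performance analysis". The same pair of statements stands in protocol 15.5 and in the Statistics part of the protocol synopsis.

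The Per Protocol Analysis Set (PPAS) is described as "a subset of PAS excluding subjects with protocol violation and major protocol deviation(s) that may impact the primary endpoint assessment". SAP 7.9 assigns the primary test to these two sets: "Primary endpoint will be measured using Performance Analysis Set; a confirmatory analysis of primary endpoint will be run using Per Protocol Analysis Set". The only hernia analysis on all enrolled subjects is a descriptive one: "Time to incisional hernia occurrence: will be measured using Kaplan Meier estimates, and based on SAS, and PPAS". In that line SAS means the Safety Analysis Set.

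On missing outcomes, protocol 15.1 says "The main analysis of the study objectives will be based on available data and missing data will not be imputed" and SAP 7.4 says "No data imputation will be performed for missing data unless otherwise noted in statistical analysis plan", each subject to exceptions noted in the SAP. The SAP notes none for this situation.

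**The concern.** The sentence removes a person; the footnote removes part of a person's data. Both cannot operate, because a subject outside the set has no data left to truncate. No section says which one the programmer should follow.

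The trigger is also not separate from the outcome. The term unscheduled is not defined, and repair of an incisional hernia is not exempted from abdominal surgery. Protocol 5.1 itself notes that incisional hernias can obstruct, incarcerate or strangulate, and that repair needs a further procedure. A subject can therefore meet the trigger because the primary endpoint has occurred.

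The set carries the comparison of a single arm with a fixed 20%, so no control group shares the loss. The PPAS is nested in the PAS and inherits the rule, so it is no check on it. If the choice stays open, it will be made in an open-label study with outcomes already known.

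**Working it through.** **1. The plan's own figure.** Inputs from SAP 6 and protocol 15.6: 20% reference rate, 10% assumed rate with mesh, two-sided 5%, power 80%.

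n = [(1.960 × √(0.2 × 0.8) + 0.842 × √(0.1 × 0.9)) / 0.10]² = 107.4, rounded up to 108. With 20% attrition, 108 / 0.80 = 135. Both stated figures reproduce.

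**2. The decision boundary.** Let c(n) be the largest count k with P(X ≤ k | n, 0.20) ≤ 0.025. Then c(108) = 13, with exact size 2.1% and power 81.0% at a true 10%. The exact two-sided p is twice the lower tail. The normal approximation uses z = (x/n − 0.20) / √(0.16/n).

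| Result | Rate | Exact p | Normal p |
|---|---|---|---|
| 14/108 | 13.0% | 0.078 | 0.068 |
| 13/107 | 12.1% | 0.047 | 0.042 |

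Dropping one subject with a hernia turns failure into success under both tests. If one hernia-free subject is also dropped, 13/106 fails on the exact test only (p = 0.052); the normal approximation gives 0.046. The plan names a binomial one-way test without saying which form.

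**3. What each rule does with a hernia.**

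| Hernia first documented | Sentence (exclude subject) | Footnote (truncate) |
|---|---|---|
| Before the operation | lost | kept |
| At the operation | lost | lost |

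**4. False success under whole-subject exclusion.** The documents give no shares, so these are assumptions. Let r be the share of hernias and q the share of hernia-free subjects excluded, with a true rate of 20% and 108 evaluable before exclusion. The number removed is D ~ Bin(108, 0.2r + 0.8q). The remaining rate is p = 0.2(1 − r) / (1 − 0.2r − 0.8q), which is below 20% only if r > q. False success is the sum over D of P(D) × P(X ≤ c(108 − D) | 108 − D, p).

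| | r = 10% | r = 20% | r = 30% |
|---|---|---|---|
| q = 0 | 4.4% | 10.1% | 21.0% |
| q = 5% | 2.9% | 7.0% | 15.7% |
| q = 10% | 1.8% | 4.8% | 11.4% |

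**5. False success under truncation.** Suppose 10/20/30% of hernias are reoperated and one fifth of those are first documented at the operation (also assumed). The lost share of hernias is then 2/4/6%. Here q is the share of hernia-free subjects who leave because they are truncated without a 24-month assessment.

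| | lost 2% | lost 4% | lost 6% |
|---|---|---|---|
| q = 0 | 2.6% | 3.0% | 3.4% |
| q = 5% | 1.3% | 1.6% | 1.9% |
| q = 10% | 0.8% | 0.9% | 1.2% |

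**6. Counting every hernia while truncated hernia-free subjects leave.** A true 20% then reads 0.2 / (0.2 + 0.8(1 − q)) = 20.8% at q = 5% and 21.7% at q = 10%. At a true 10% the observed rate is 0.1 / (0.1 + 0.9(1 − q)) = 10.5% or 11.0%. Power, P(X ≤ 13 | 108, that rate), falls from 81.0% to 76.1% or 70.3%, with 108 still evaluable.

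**The case against.** The best defence is that the asterisk makes the footnote an instruction for applying the sentence. The footnote has no function if the subject is already gone, so the two together mean truncation. The clause about raised hernia risk, and protocol 12.1 on pregnancy as a risk factor, suggest the authors had causes of a later hernia in mind. Much of this stands: truncation is the more natural rule, and under it a hernia documented before the operation is kept. What remains is that the words of the sentence say otherwise, and that a hernia first found at the operation falls within the removed data.

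A reader might infer that the rule biases the trial in favour of the mesh. The documents do not support that. The larger false-success figures need whole-subject exclusion and few exclusions among hernia-free subjects. With 10% of both groups excluded the figure is 1.8%, and under truncation with 5% of hernia-free subjects leaving it is 1.3/1.6/1.9%, all below the nominal 2.1%.

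A reader might also take protocol 11.13.1, which uses all data up to study exit, as settling the matter for truncation. It does not. Neither pregnancy nor reoperation as such is a listed exit reason, so that section is in tension with truncation too.

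Finally, the problem would not be wholly invisible. SAP 7.1.1 promises that subjects "in the Performance Analysis Set (PAS) and in the Per Protocol Analysis Set (PPAS) will be summarized, according to follow-up", and the Kaplan-Meier estimate covers everyone enrolled. But neither tests the hernia rate against 20%.

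**Conclusion.** The concern holds as an undefined rule in the primary analysis that can remove true primary-endpoint events. On the literal sentence it removes the whole subject; under the footnote it removes only a hernia first documented at the operation. One such subject at the boundary is enough to change the conclusion, whichever form of binomial test is used.

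The likely size is not established under either reading, and at low shares neither is the direction. Every false-success figure rests on assumed shares, a true rate of 20%, 108 evaluable subjects and the exact test. The reason to act is that the rule is ambiguous and can be triggered by the outcome, not that a particular inflation has been shown. It should be fixed; the sample size of 108 evaluable and 135 enrolled is not in question.

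**What to change.** Before the 24-month data are analysed, change SAP 7.1.3, protocol 15.5 and the synopsis together:

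1. State that truncation at the event is the only rule, and delete the whole-subject exclusion.
2. State that an incisional hernia diagnosed before or at a reoperation, including its repair, counts as a primary-endpoint event, and that incisional hernia repair is not an excluding surgery.
3. Add one sensitivity analysis of the primary endpoint on all enrolled subjects with all follow-up, tested against 20%.
4. State how a subject truncated without a hernia and without a 24-month assessment is handled in the main analysis, and report the alternative handling beside it. The available-data wording points to not evaluable but does not say so.

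Item 4 is a real trade-off: leaving those subjects out while counting every hernia raises the observed rate and lowers power, as step 6 of the working shows. Subjects lost this way also draw on the attrition allowance of 135 − 108 = 27. Otherwise the cost is wording in three places, one extra table and a slightly less favourable observed rate.
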